9.4.1.2 Baseline Ophthalmic Testing (Visit 1a)

Ophthalmic assessment at Visit 1a may occur at any time during the Screening period.

Ophthalmic assessments include:

- BCVA using the LogMAR chart (i.e. after manifest refraction)
- IOP (preferably measured by Goldmann tonometry before and after dilation with mydriatic agent)
- Corneal staining
- Slit lamp examination
- Lenticular opacification using LOCS III

9.4.2 Baseline (Visit 2)

- NIH-CPSI
- Paper-based 11-point NRS
- PHQ-9
- IIEF
- PGI-S
- Review Inclusion/Exclusion criteria
- eDiary review for Inclusion/Exclusion criteria
- Physical examination
- Vital signs (HR, BP, temperature)
- Clinical chemistry (does not need to be fasting), hematology, urinalysis
- Voiding frequency measured over a 24-hour period, within a 3-day (72 hours) window before the scheduled Visit
- AE collection
- Review concomitant medication
- Randomization after confirming subject continues to meet eligibility criteria
- Study drug dispensing
- Administration of first dose of study drug (after all assessments performed)

9.4.3 Treatment Period

9.4.3.1 Visit 3

- NIH-CPSI
- Paper-based 11-point NRS
- PHQ-9
- GRA
- PGI-C
- IIEF
- PGI-S
- Voiding frequency measured over a 24-hour period, within a 3-day (72 hours) window before the scheduled visit
- Vital signs (HR, BP, temperature)
- AE collection
- Review concomitant medication
- Study drug dispensing
- Study drug compliance check
- Study drug accountability
- eDiary review

9.4.3.2 Visit 4

- NIH-CPSI
- Paper-based 11-point NRS
- PHQ-9
- GRA
- PGI-C
- IIEF
- PGI-S
- Voiding frequency measured over a 24-hour period, within a 3-day (72 hours) window before the scheduled visit
- Physical examination
- Ophthalmic assessments (BCVA, IOP, corneal staining, slit lamp, LOCS III)
- 12-lead supine ECG
- Vital signs (HR, BP, temperature)
- Weight
- Clinical chemistry (does not need to be fasting), hematology, urinalysis
- AE collection
- Review concomitant medication
- Study drug compliance check

- Study drug accountability
- eDiary review

9.4.4 Early Termination

- NIH-CPSI
- Paper-based 11-point NRS
- PHQ-9
- GRA
- PGI-C
- IIEF
- PGI-S
- Voiding frequency measured over a 24-hour period, within a 3-day (72 hours) window before the scheduled visit
- Physical examination
- Ophthalmic assessments (BCVA, IOP, corneal staining, slit lamp, LOCS III)
- 12-lead supine ECG
- Vital signs (HR, BP, temperature)
- Weight
- Clinical chemistry (does not need to be fasting), hematology, urinalysis
- AE collection
- Review concomitant medication
- Study drug compliance check
- Study drug accountability
- eDiary review

9.4.5 Safety Follow-up

9.4.5.1 Off-Treatment Safety Follow-up

- NIH-CPSI
- Paper-based 11-point NRS
- PHQ-9
- GRA
- PGI-C
- IIEF
- PGI-S
- Voiding frequency measured over a 24-hour period, within a 3-day (72 hours) window before the scheduled visit
- Physical examination (only needed if there are outstanding safety concerns from Week 12)

- Ophthalmic assessments (only needed if there are outstanding safety concerns from Week 12)
- 12-lead supine ECG (only needed if there are outstanding safety concerns from Week 12)
- Vital signs (HR, BP, temperature)
- Weight
- Clinical chemistry (does not need to be fasting), hematology, urinalysis (only needed if there are outstanding safety concerns from Week 12)
- AE collection
- Review concomitant medication
- eDiary review/collect

9.4.5.2 Telephone Call

- AE collection (ophthalmic related AEs only)

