Abbreviations: AE=adverse event; BCVA=best corrected visual acuity; BP=blood pressure; C=collect; ECG=electrocardiogram; eDiary=electronic diary; ET=Early Termination; GRA=Global Response Assessment; HR=heart rate; I=issue; IIEF =International Index of Erectile Function; IOP=intraocular pressure; LOCS= Lens Opacity Classification System; LogMAR=Logarithm of the Minimum Angle of Resolution; NA=not applicable; NIH-CPSI=National Institute of Health Chronic Prostatitis Syndrome Index; NRS=Numerical Rating Scale; PCS=Pain Catastrophizing Scale; PGI-C=Patient’s Global Impression of Change scale; PGI-S=Patient’s Global Impression of Severity scale; PHQ-9=Patient Health Questionnaire; R=review; T=train; UPOINT=Urinary, Psychosocial, Organ Specific, Infection, Neurologic/Systemic, Tenderness of Skeletal Muscles.

- ^a Minimum screening period is 7 days, which includes the baseline ophthalmic assessment at Visit 1a.
- ^b Demographics include age, birth year, sex, race and ethnicity.
- ^c Questionnaires must be completed prior to other assessments.
- ^d Paper-based 11-point NRS will be administered in-clinic during the study visit to assess the average and maximum daily pelvic pain.
- ^e Ophthalmic assessments include BCVA using the LogMAR chart (i.e. after manifest refraction), IOP (preferably measured by Goldmann tonometry, before and after dilation with mydriatic agent) corneal staining, slit lamp examination, and lenticular opacification using LOCS III. Baseline ophthalmology assessment can be completed as a separate visit any time during the screening period (any time before Visit 2). Background incidence of cataracts in subjects noted prior to dosing should be recorded as medical history. Ophthalmic assessments at all post-Baseline Visits should occur within the specified Visit windows.
- ^f Subjects will be resting supine for at least 5 minutes before the ECG recording.
- ^g Clinical chemistry does not need to be fasting.
- ^h Voiding frequency will be measured over a 24-hour period, within a 3-day (72 hours) window before the scheduled visits.
- ⁱ The first dose of study drug at Baseline (Visit 2) will be administered in the clinic. At subsequent Visits, subjects are to refrain from taking study drug at home on the morning of the clinic visit day and should be dosed in the clinic.
- ^j If a subject withdraws from the study, all assessments for the ET Visit should be conducted.

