- ^k Subjects who withdraw from the study anytime during the study will have a follow-up period of 6 months, consisting of an Off-Treatment Safety Follow-up Visit (4 weeks post last dose), telephone call follow-up (3 months post last dose) and ophthalmic assessment (6 months post last dose).
- ^l Subjects will be asked for updates on new and ongoing (after the 28 days follow-up) ocular AEs only.
- ^m Repeat at Off-Treatment Safety Follow-up is only needed if there are outstanding safety concerns from Week 12.
- ⁿ Score will not be recorded in the database, assessment will be performed for patient safety/monitoring purposes only clinically significant findings will be reported as adverse events.

NOTE: Unscheduled visits may be conducted at any time during the study and may include the same assessments as Week 12.

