- A series of repeat dose toxicity studies in the rat have been conducted for durations of 7 days up to 26 weeks. In the 26-week rat study, the no observed adverse effect level (NOAEL) was 30 mg/kg/day, based on the findings in females of bilateral posterior cortical cataracts and microscopic lens swelling/cataracts, persistent estrous characterized by the interrelated effects to the reproductive tract and mammary glands, and findings in males of reduced caudal epididymal sperm density and counts and epididymal epithelial microvesicular vacuolation at 100 mg/kg/day. At the NOAEL, the mean maximum observed plasma concentration (C_{max}) and area under the plasma concentration–time curve from time 0 to 24 h (AUC_{0-24}) values were 1110 ng/mL and 7100 ng•hr/mL, respectively, in males and 1580 ng/mL and 9940 ng•hr/mL, respectively, in females.
- A series of repeat dose toxicity studies in the dog have been conducted for durations of 10 days up to 39 weeks. In the 39-week dog study, daily administration of AQX-1125 at dose levels of 10, 30, and 50 mg/kg/day resulted in no adverse findings. At the NOAEL of 50 mg/kg/day, the mean C_{max} and AUC_{0-24} values were 6160 ng/mL and 59,300 ng•hr/mL, respectively, in males and 6820 ng/mL and 69,300 ng•hr/mL, respectively, in females.
- No mutagenic potential was observed for AQX-1125 in the bacterial mutation, chromosome aberration, or rat micronucleus tests.
- AQX-1125 had no effect on rat male or female fertility or on early embryonic development at doses up to the highest dose tested of 300 mg/kg/day.
- AQX-1125 was teratogenic in rats, but not in rabbits. The rat embryo-fetal development NOAEL was 30 mg/kg/day (C_{max} 439 ng/mL; AUC_{0-24} 4,710 ng•hr/mL) based on teratogenic effects (external, soft tissue and skeletal malformations and variations and delays in skeletal ossifications) observed at doses ≥100 mg/kg/day. In rabbits, AQX-1125 was not teratogenic at the highest dose tested of 80 mg/kg/day (C_{max} 16,000 ng/mL; AUC_{0-24} 78,700 ng•hr/mL).
- AQX-1125 caused reduced pup viability at doses ≥75 mg/kg/day including increases in dams with no live born pups (150 mg/kg/day), pups dying within the first 4 days after birth and stillborn pups. The deaths occurring in the late stage of gestation/shortly after parturition was suggestive of stress and/or physiological changes associated with the late stage of pregnancy. At 75 mg/kg/day, the F0 dams had body weight loss in lactation days

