7.1 Inclusion Criteria

For inclusion into the screening period subjects must meet the following criteria:

1. Provide written informed consent and the willingness and ability to comply with all aspects of the study requirements
2. Males, ≥ 18 and ≤ 80 years of age at Screening Visit 1
3. Have pain or discomfort in the pelvic region for at least 3 months in the last 6 months, in the absence of a urinary tract infection or other pelvic/urological cause, and have a physician diagnosis of CP/CPPS (NIH Prostatitis, Category III)
4. NIH-CPSI of ≥ 15 on the total score
5. Subjects must agree to use a condom for sexual intercourse from Screening Visit 1 until at least 90 days after the last dose of study drug, unless they have been surgically sterilized (vasectomy) for a minimum of 6 months. True abstinence from sexual intercourse in accordance with the preferred and usual lifestyle of the subject is also acceptable
6. Have an average daily pelvic pain score of ≥ 4 out of 10 on the 11-point NRS pain scale (mean of the average daily pelvic pain score recorded at each of the 7 days prior to Baseline [Visit 2]). A minimum of 5 daily records within 7 days prior to Baseline (Visit 2) must be recorded
7. Must be capable of voiding independently for 30 days prior to screening (to allow completion of 24-hour voiding diary)

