9.3.5.6 Recording Adverse Events

For the purposes of this study, any detrimental change in the subject's condition, from signing of informed consent up to completion of the treatment period should be considered an AE (i.e. for up to 28 days after last dose of investigational product has been taken).

AEs should be captured wherever possible as a diagnosis and it is the Investigator's responsibility to ensure this is done. If a precise diagnosis cannot be made, a syndrome can be recorded. Rarely should it be necessary to record one or more individual symptoms.

All ongoing non-ocular AEs should be followed up until the Off-Treatment Safety Follow-up Visit (for 28 days after the last administration of study drug), with the exception of any ongoing study drug-related AEs, which should be followed until resolution, unless in the Investigator's opinion the AE is unlikely to resolve due to the subject's underlying disease. Ongoing ocular AEs will be queried at the Follow-up call 3 months post last dose and at the Ophthalmic Safety Follow-up Visit 6 months post last dose.

Ocular AEs must be followed until the 6-month Ophthalmic Safety Follow-up Visit.

Any new SAEs occurring up to 28 days after the last administration of study drug should be reported to the drug safety manager.

At any time after the Off-Treatment Safety Follow-up Visit, if an Investigator learns of an SAE that can be reasonably related to study drug, he/she should promptly notify the drug safety manager.

All AEs (including SAEs) are to be accurately recorded on the Adverse Event page(s) of the eCRF. The Investigator will carefully evaluate each AE to determine:

- duration (start and end dates)
- intensity (grade)
- seriousness
- relationship to study drug (Unlikely, Possible, Probable)
- action taken with study drug (study drug modification or interruption, study drug discontinuation)
- action taken (none, medication, medical intervention)
- outcome (resolved without sequelae, resolved with sequelae, ongoing)

The Investigator will evaluate all AEs and SAEs with regard to maximum intensity and relationship to study drug. Maximum intensity should be assigned using one of the severity grades as outlined in the National Cancer Institute's Common Terminology Criteria for Adverse Events v4.0. If the AE is not specifically listed in Common Terminology Criteria for Adverse Events v4.0, the following grades will be used:

- Grade 1: mild
- Grade 2: moderate
- Grade 3: severe

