9.3.5.8 Reporting Deaths and Other Serious Adverse Events

9.3.5.8.1 Events to Be Reported and Timeframe

Any death or other SAE experienced by the subject during treatment or within 30 days of receiving study drug, regardless of relationship to study drug, or any death that occurs more than 28 days after receiving study drug and is believed to be study drug-related, must be promptly reported to the Sponsor (*within 24 hours of the Investigator becoming aware of the event*) by telephone, telefax, or e-mail transmission.

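### SAE windows and off-treatment visit timing conflict, so the last scheduled non-ocular AE question can fall 22 days after last dose; partner pregnancy is never asked about

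*Protocol*

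**What the plan says.** **SAE window.** Protocol 9.3.5.6 states: "Any new SAEs occurring up to 28 days after the last administration of study drug should be reported to the drug safety manager". Protocol 9.3.5.8.1 requires prompt reporting of deaths and other SAEs arising "during treatment or within 30 days of receiving study drug, regardless of relationship to study drug", then uses 28 days in the same sentence for late deaths believed to be drug-related. Section 9.3.5.4.1 also uses 28 days for deaths. SAP 2.2.15.2 counts events other than ocular events of special interest as treatment-emergent only if onset is within 28 days of last dosing.

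**Timing of the last general AE question.** Section 9.4.5.1 lists unrestricted AE collection at the Off-Treatment visit. Table 1 puts that visit at Day 112 ±3 and Visit 4 at Day 84 ±3. Table 1 footnote k describes follow-up instead as "consisting of an Off-Treatment Safety Follow-up Visit (4 weeks post last dose"), and sections 6.1 and 7.4 also time the visit from stopping study drug. Footnote i says subjects do not take drug at home "on the morning of the clinic visit day and should be dosed in the clinic", so the last dose can fall on the day of Visit 4.

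**Later contacts.** Section 9.4.5.2 gives the content of the 3-month call as "AE collection (ophthalmic related AEs only"). Section 9.4.5.3 adds an eye examination at 6 months but limits AE collection in the same way. Table 1 footnote l says: "Subjects will be asked for updates on new and ongoing (after the 28 days follow-up) ocular AEs only". SAP 2.2.2 repeats the restriction.

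**Reproductive provisions.** Section 7.1 requires condoms from screening "until at least 90 days after the last dose of study drug", with exceptions for vasectomy and abstinence. Section 4.2.1 reports that "AQX-1125 was teratogenic in rats, but not in rabbits". No section, visit list or contents entry provides for asking about, reporting or following a partner's pregnancy.

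**The concern.** A reporting window works only if someone asks about events until it closes, or if the plan accepts that it relies on volunteered reports. Here the last scheduled general question can come before either stated window closes, and the next two contacts are confined to eyes. The subject is therefore spoken to again at about 3 months without being asked about a hospital admission in week 4 after the last dose. The same visit feeds the SAP's 28-day treatment-emergent window, so non-serious events are exposed too. Both arms follow the same schedule, so the expected effect is under-counting in both rather than a bias between them.

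The conflicting windows are a separate fault. Two sites reading different sections could handle an SAE on day 29 or 30 differently.

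On pregnancy, the sponsor imposes a contraceptive precaution but collects nothing on whether it failed. A partner's pregnancy is not a change in the subject's own condition, so the AE recording rule in 9.3.5.6 does not clearly reach it. A birth defect is listed as an SAE outcome in 9.3.5.4.1, yet no scheduled contact would bring one to light.

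**Working it through.** **Inputs (Protocol Table 1)**
- Visit 4: Day 84 ±3, so Days 81 to 87
- Off-Treatment visit: Day 112 ±3, so Days 109 to 115
- Telephone call: Day 175 ±7, so Days 168 to 182
- Ophthalmic visit: Day 266 ±7, so Days 259 to 273
- Last dose taken in clinic on the Visit 4 day (Table 1 footnote i; section 8.3). Section 8.6 provides spare doses so that treatment continues if a visit runs late within its window, so a last dose on Day 87 is foreseen.

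**1. Reproduce the plan's intervals on target days**
- 112 − 84 = 28 days, matching the stated 4 weeks
- 175 − 84 = 91 days (13 weeks), matching 3 months
- 266 − 84 = 182 days (26 weeks), matching 6 months

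**2. Apply the visit windows to the last general AE question**
- Earliest: 109 − 87 = 22 days after last dose
- Latest: 115 − 81 = 34 days
- If the last dose is instead the day before Visit 4, the range is 23 to 35 days.

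**3. Compare with the two SAE windows**

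| Off-Treatment visit | Days after last dose | Short of 28 | Short of 30 |
|---|---|---|---|
| Table 1, earliest | 22 | 6 | 8 |
| 4 weeks after last dose, if ±3 applied to it (assumed) | 25 | 3 | 5 |
| On target | 28 | 0 | 2 |

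The third decimal of precision is not at issue here; what matters is the spread. Each window has 7 permitted days, giving 7 × 7 = 49 pairs of visit days. Of these, 21 give fewer than 28 days and 34 give fewer than 30. These are counts of permitted combinations, not probabilities.

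**4. The later contacts**
- Call: 168 − 87 = 81 to 182 − 81 = 101 days after last dose. It can fall 90 − 81 = 9 days before the minimum condom period ends.
- Ophthalmic visit: at the earliest 259 − 87 = 172 days, always after day 90.

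**5. Partner pregnancy (no arithmetic applies)**
The visit lists in 9.4.1 to 9.4.5, Table 1, the AE and SAE sections under 9.3.5 and the table of contents contain no question, form, reporting route or follow-up for a partner's pregnancy. The nearest text is the birth-defect item in the SAE definition.

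**The case against.** A reader might infer that AE collection stops 22 days after last dose. The documents do not support that. Section 9.3.5.6 keeps AE recording and SAE reporting open to 28 days, 9.3.5.8.1 extends SAE reporting to 30, and an SAE reasonably related to study drug must be notified whenever the investigator learns of it. Unscheduled visits are allowed at any time. Only scheduled, active questioning can stop early.

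The 22 days is also the extreme. It needs a late Visit 4 and an early follow-up visit, 1 of the 49 pairs, and 28 of the 49 reach 28 days or more. Several sections time the visit 4 weeks after last dose, which leaves no shortfall against 28 days on target. Both points stand, but neither removes the conflict between the two timings or the 2-day shortfall against the 30-day window on target.

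A reader might also infer a reproductive hazard through treated men. The documents do not show one. Section 4.2.1 reports no teratogenicity in rabbits, no mutagenic potential, and no effect on rat male or female fertility or early embryonic development. It gives no data on exposure through a male partner. It does report accumulation in rat testes, high levels in rat seminal vesicles, and reduced epididymal sperm counts at 100 mg/kg/day in the 26-week rat study, so the precaution has a stated background. With roughly 50 men on active drug and condoms required, collecting pregnancies would be unlikely to establish or exclude a risk. Its purpose is to report and follow individual cases.

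Finally, a question at 3 months relies on recall: on target days, an event at day 28 is asked about 91 − 28 = 63 days later. That is a real limitation, and it is why the visit timing also needs settling.

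**Conclusion.** The point holds as a safety-collection gap and an internal contradiction. The SAE windows (28 and 30 days) and the timing of the Off-Treatment visit (study day or time since last dose) each need reconciling. Under the Table 1 windows the last scheduled non-ocular question comes 22 to 34 days after last dose: at worst 6 days short of the 28-day window and 8 short of the 30-day window, and on target 0 and 2. Events after that visit remain reportable but depend on unsolicited reports.

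Partner pregnancy is not collected at any scheduled contact. That is an omission in the collection plan, not evidence of harm.

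These conclusions assume that the last dose is taken at Visit 4, that the 30-day window runs from last dose, and that study manuals or forms outside these two documents do not already supply the missing questions. No efficacy analysis is affected. The change is worth making because the contacts already exist and, as written, these events go uncollected unless volunteered.

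**What to change.** 1. Reconcile the 28- and 30-day windows across Protocol 9.3.5.4.1, 9.3.5.6 and 9.3.5.8.1, and check that the treatment-emergent definition in SAP 2.2.15.2 agrees with the result. Which window applies is for the sponsor to decide.
2. Reconcile the two timings of the Off-Treatment visit (Table 1 against footnote k and sections 6.1 and 7.4), stating the reference date and the permitted window together.
3. Amend 9.4.5.2, 9.4.5.3 and Table 1 footnote l, with the matching text in SAP 2.2.2. The 3-month call should also ask about any AE or SAE with onset inside the reconciled window, and about partner pregnancy.
4. Repeat the pregnancy question at the 6-month visit, because the call may come before day 90.
5. Send any partner pregnancy to the Drug Safety Manager and follow it to outcome with the partner's consent.

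Cost: two added questions, one report form and one partner consent form, a little site time and perhaps a few extra reports. There is no new visit. Recall of about two months limits what the call can recover.

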9.4.5.3 Ophthalmic

- Ophthalmic assessments
- AE collection (ophthalmic related AEs only)

9.4.5.4 Unscheduled Visit

Unscheduled visits may be conducted at any time during the study and may include the same assessments as Week 12 (Visit 4).

10 STATISTICAL METHODS AND PLANNED ANALYSES

Statistical methods and conventions are described in this section. Full details on the analysis methods and presentation of study results will be provided in the statistical analysis plan (SAP). The SAP will be finalized prior to unblinding of the trial.

10.1 General Considerations

All statistical analyses will be performed using SAS® Version 9.4 or higher.

All clinical study data will be presented in subject data listings. Descriptive statistics (n, mean, standard deviation, median, minimum, and maximum) will be calculated by treatment group for continuous variables. Confidence intervals (CIs) will be provided where appropriate.

Frequencies and percentages will be presented by treatment group for categorical and ordinal variables.

Means, medians, and CIs will be reported to 1 decimal place more than the data reported on the eCRF or by the laboratory/vendor. Standard deviations will be reported to 2 decimal places more than the data reported. Minimum and maximum will be reported to the same number of decimal places displayed on the eCRF or by the laboratory/vendor. *P* values will be reported to 4 decimal places.

